11.1 Inclusion Criteria

Every eligible patient at participating investigational sites must meet the following criteria:

Inclusion criteria:

1. Male and female patients 18 years or older by the time of enrolment
2. Confirmed diagnosis of Crohn's disease or ulcerative colitis for at least 2 years prior to enrolment in the study.
3. The presence of a moderate to severe IBD flare at the time of enrolment or in patient anamnesis within 2 years before enrollment treated with steroids or/ and immunosuppressive agents or/ and biologic therapy. IBD flare(s) must be confirmed in the source documentation.
4. Current treatment with steroids or/ and immunosuppressive agents or/ and 5-ASA or/ and biologic therapy
5. Written informed consent, signed before the participation in the study begins.

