12.2 Tabulated overview of data collection

The documentation of study data will be reported by investigators via electronic case report form (eCRF).

Assessment / Procedure	Retrospective data collection*	Baseline visit (V1, Day 1)	Observational visit (V2, Month 6)	Final visit (V3, Month12)
Informed consent		X		
Patients' eligibility assessment: Inclusion/exclusion criteria		X		
Date of visit		X	X	X
Demographics data		X		
Disability		X		
Physical examination		X	X	X
Medical history / Concurrent medical conditions	X	X		
History of IBD	X	X		
IBD family history		X		
IBD assessment	X	X	X	X
Disease activity data		X	X	X
IBD status		X	X	X
Laboratory and instrumental evaluation of IBD **	X	X	X	X
IBD treatment	X	X	X	X
Healthcare resources utilization	X	X	X	X
Concomitant treatment		X	X	X
Physician Survey		X		X
Adverse events			X	X

* Retrospective data within two years before of patient enrolment in the study will be collected at Visit 1 after the signing of the informed consent form

**All examinations (laboratory tests and instrumental exams) are done in accordance with clinical routine practice and physician's decision. All examinations results should be registered in electronic CRF only if they are done in routine practice.

12.3 Data collected on the Baseline visit (V1), including collection of Retrospective data within two years before of patient enrolment in the study

The baseline visit takes place at the physician's office. Data to be collected:

- Date of Informed consent form signing (day, month, year);
- Inclusion/exclusion criteria;
- Date of visit (day, month, year);
- Demographics data (gender, date of birth, ethnicity, region of residence, smoking status, employment status (employed, unemployed, retired, student, other));
- Disability:
 - Disability group
 - Cause of disability
 - Year of disability
- Physical examination: height (cm) and weight (kg), body mass index calculation;
- Medical history/Concurrent medical conditions (disease, date of diagnosis, resolution date);
- History of inflammatory bowel disease (IBD):
 - Type of inflammatory bowel disease (ulcerative colitis (UC) or Crohn's disease (CD)),
 - Date of IBD diagnosis,
 - Date of IBD symptoms onset,
 - Availability of observation in the current investigational site within previous 2 years
- IBD family history (degree of relationship);
- Clinical course of IBD (acute, chronic continuous, chronic recurrent);
- IBD assessment for the last 2 years and at the time of the baseline visit:

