12.7 Laboratory and instrumental examinations to be documented in the study

All examinations (physical examination and vital signs, laboratory tests and other exams) will be performed in accordance with common clinical routine practice, routine practice of a particular medical institution. All examinations are solely based on the physician's decision about strategy of diagnostics and treatment.

The following laboratory and instrumental examinations are planned to collect in the study:

- Laboratory tests results
 - Biomarkers: CRP, faecal calprotectin
 - Immunological tests: TB diagnostic test
- Endoscopic examination/ biopsy of GI tract
- X-ray of GI tract and lungs
- MRI/CT examination related to IBD
- Ultrasound examination related to IBD

All laboratory and instrumental examinations are collected during all period of data collection: retrospectively, at Baseline visit, through 1 year of prospective observation.

12.8 Documentation of Medical history and Concurrent Medical Conditions.

Medical history is history of diseases indicated before signing of the Informed Consent Form.

Concurrent medical conditions are those significant (ongoing conditions or diseases that are present at signing of informed consent). Concurrent medical conditions may include not limited to tuberculosis, cardiovascular disorders, diabetes, chronic pulmonary artery disease, chronic kidney disease. The condition (i.e., diagnosis) should be registered in eCRF.

Time of medical event/disease	How it should be documented
Before ICF signed	Medical history
At the moment of ICF signing	Concurrent medical conditions
After ICF signing	Adverse Events

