- Laboratory and instrumental evaluation of IBD for the last 2 years and at the time of the baseline visit (if done within routine practice);
- IBD treatment:
  - IBD treatment for the last 2 years and at the time of the baseline visit;
  - IBD surgical treatment for the last 2 years and at the time of the baseline visit;
- Healthcare resources utilization for the last 2 years and at the time of the baseline visit;
- Concomitant treatment.

Protocol ID	MACS-2017-102279	STATISTICAL ANALYSIS PLAN	Page 12 of 41	
IP	N/A		Date	30.12.2021
ID	MACS-2017-102279_SAP		Version	v1.2 final

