### 5.3.3 Collection of data on the continuous basis

All data described below should be collected through whole observational prospective 1-year period of patients within the periods: Baseline visit -Visit 2, Visit 2 - Visit3 (independently of actual number of patient's visit to the clinic):

- IBD treatment;
- IBD surgical treatment (indications, types of surgeries, complications, presence of stoma, etc.);
- Results of diagnostic methods used (within the period since last visit);
- Healthcare resources utilization;
- Concomitant treatment;
- Adverse events and adverse drug reactions (seriousness, severity, causality, start and stop dates, action, frequency, outcomes):
  - adverse drug reactions on IBD treatments, ○ adverse events on Entivyo® (Vedolizumab) treatment,
  - serious adverse events on IBD treatments (including Entivyo® (Vedolizumab) treatment).

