### Subgroups of first-line biological therapy

1. Vedolizumab
  - a. By the period of time from diagnosis to biological therapy prescription:
    - up to 2 years inclusive
    - from 2 to 5 years inclusive
    - more than 5 years
  - b. By the number of courses of systemic corticosteroids in medical history before biological therapy prescription:
    - < 3 courses
    - ≥ 3 courses

Protocol ID	MACS-2017-102279	STATISTICAL ANALYSIS PLAN	Page 18 of 41	
IP	N/A		Date	30.12.2021
ID	MACS-2017-102279_SAP		Version	v1.2 final

c. Depending on disease activity at the moment of biological therapy prescription:

- Crohn's disease, the Harvey-Bradshaw index:

- < 5 points
- 5-16 points
- >16 points

- Ulcerative colitis, the Partial Mayo Score:

- 0 scores
- 1-2 scores
- 3-5 scores
- ≥ 6 scores

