**Depending on surgical treatment within ≤ 2 years before biological therapy prescription:**

- a. Surgical patients
  - With post-operative anti-relapse biological therapy (CD)
  - Without post-operative anti-relapse biological therapy (CD)
- b. Non-surgical patients

Protocol ID	MACS-2017-102279	STATISTICAL ANALYSIS PLAN	Page 21 of 41	
IP	N/A		Date	30.12.2021
ID	MACS-2017-102279_SAP		Version	v1.2 final

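### The steroid-course and surgery splits in SAP 7.4 need a look-back before the biologic that the recorded window often does not cover, and the default error runs towards '<3 courses' and 'non-surgical'

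*SAP*

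**What the plan says.** **Subgroup definitions (SAP 7.4).** The steroid split, repeated for each first-line drug, is "By the number of courses of systemic corticosteroids in medical history before biological therapy prescription", with cut-points <3 and ≥3 and no time limit. The surgical split is headed "Depending on surgical treatment within ≤ 2 years before biological therapy prescription". Both count backwards from the biologic.

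**Data collected.** Collection counts backwards from enrolment. Protocol 12.2 states that "Retrospective data within two years before of patient enrolment in the study will be collected at Visit 1". SAP 5.3.1 and Protocol 12.3 list "IBD treatment for the last 2 years and at the time of the baseline visit" and "IBD surgical treatment for the last 2 years and at the time of the baseline visit". SAP 5.3.3 adds continuous recording over the prospective year of IBD treatment and of "IBD surgical treatment (indications, types of surgeries, complications, presence of stoma, etc".

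**Other possible sources.** Protocol 12.8 limits medical history to illnesses: "Medical history is history of diseases indicated before signing of the Informed Consent Form". The IBD history items in Protocol 12.3 are disease type, dates of diagnosis and symptom onset, and whether the site followed the patient in the previous 2 years. None of these holds a count of steroid courses or a list of earlier operations.

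**The concern.** The subgroups are anchored on one date and the data on another. A patient who began a biologic 20 months before enrolment has 4 months of recorded steroid and surgical history before it. A patient already on the biologic when the window opened has none. Such patients are eligible: Protocol 11.1 accepts current biologic treatment and requires "Confirmed diagnosis of Crohn's disease or ulcerative colitis for at least 2 years prior to enrolment in the study", and SAP 7.4 itself has a stratum for more than 5 years from diagnosis to biologic.

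A course or operation before the window is not a blank field that a query would find. It is simply absent. With only two levels in each split, the natural programming result is '<3 courses' and 'non-surgical'. Membership then depends partly on when the biologic was started relative to enrolment, and a difference in remission or failure between the rows could be read as an effect of steroid burden or surgery when it partly reflects time on the biologic.

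**Working it through.** **The plan's own figures.** The plan gives none for these subgroups. The nearest design figure is the ±5.8-point precision in Protocol 15.4 for 288 Crohn's disease patients. It reproduces (1.96 × √(0.5 × 0.5 / 288) = 0.058) but has no bearing on classification.

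**Step 1: recorded look-back.** With retrospective recording from 2 years before enrolment, a biologic started t years before enrolment has L(t) = max(0, 2 − t) years recorded before it. A start after enrolment has more than 2 years, up to 3.

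| Biologic start | Recorded years before it | Share of the 2-year surgical look-back recorded |
|---|---|---|
| At or after Visit 1 | 2 to 3 | 100% |
| 0.5 years before | 1.5 | 75% |
| 1 year before | 1 | 50% |
| 1.5 years before | 0.5 | 25% |
| 2 or more years before | 0 | 0% |

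This step uses only the documents.

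**Step 2: direction.** Recorded courses and operations are a subset of the true ones. If absent records count as none, a true '≥3' can become '<3' and a true 'surgical' can become 'non-surgical', but not the reverse. A truncated count does no harm where the patient stays on the same side of the cut-point.

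**Step 3: surgery, illustration.** Assume a true 2-year frequency p at constant hazard, h = −ln(1 − p)/2.

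- Starts even over the 2-year retrospective window: observed = 1 − p/(−ln(1 − p)). For p = 10%: 1 − 0.10/0.1054 = 5.1%. For p = 20%: 1 − 0.20/0.2231 = 10.4%.
- Starts even over all 3 observed years: observed = (2/3) × the value above + (1/3) × p. For p = 10%: (2/3) × 5.1 + (1/3) × 10 = 6.7%. For p = 20%: (2/3) × 10.4 + (1/3) × 20 = 13.6%.
- Starts before the window: observed = 0%, which lowers either figure.

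**Step 4: steroids, illustration.** The benchmark must be the SAP's own count, which has no time limit. Assume Poisson courses at r per year over D years of disease before the biologic. Then P(≥3) = 1 − e^(−m)(1 + m + m²/2), with m = rD for the true count and m = r × (recorded years) for the observed count. Example: r = 1.0, D = 4, start at enrolment. True m = 4 gives 0.762 and recorded m = 2 gives 0.323, so 1 − 0.323/0.762 = 58% of true '≥3' patients fall in '<3'.

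| Biologic start | Share of true '≥3' placed in '<3' (r = 0.5 to 1.5, D = 4 to 6) |
|---|---|
| At enrolment | 39% to 86% |
| Even over the 2-year retrospective window | 76% to 96% |
| 2 or more years before enrolment | 100% |

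If D = 2 and the biologic starts at enrolment, nothing is lost: the whole disease history lies inside the window. The values of r, D, p and the start distributions are assumptions; the documents give none of them.

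**The case against.** **Zero by default is an inference.** A reader might infer that patients are misplaced by construction. The documents do not say how out-of-window history is counted. SAP 8.4 treats unresolved data as missing, and SAP 8.1.4 shows missing observations in table totals. That stands: the gap is the lack of a rule, not a stated zero rule. Neither section, however, would flag an event that was never recorded.

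**The prospective year counts.** A reader might infer that drugs and surgery are recorded only for the 2 years before enrolment. SAP 5.3.3 shows otherwise, and patients who start a biologic at or after Visit 1 have a complete surgical look-back.

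**The eCRF was not seen.** The stated interest in treatment histories, and the safety split by prior biologic use, suggest that some earlier treatment may be known. That limits the claim to what the documents list, and they list no source for earlier steroid courses or operations. The subgroups entered in SAP v1.2 of 30.12.2021, at the very end of the planned data-collection period (Q3–Q4 2021, Protocol 10.2), so the plan shows no route to collecting more.

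**A two-year steroid benchmark is tempting but wrong.** With starts even over the retrospective window, a true 2-year share with ≥3 courses of 32% (1.0 course per year) would appear as 11%, and 58% (1.5 per year) as 22%. The arithmetic is correct, but the SAP's steroid label is not a 2-year count, so these figures do not measure the error in its subgroup.

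**Survivor and between-drug effects are not shown.** A reader might infer that long-standing users gather in '<3 courses', or that vedolizumab, ustekinumab and anti-TNF are truncated differently. Both depend on start dates that the documents do not give. Every patient also needs a treated moderate-to-severe flare at enrolment or in the 2 years before it.

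**The splits are exploratory.** SAP 8.3 plans no tests, although SAP 8.1.1 foresees an exploratory search for associations between treatment patterns and outcomes. This lowers the stakes but does not make a row label correct.

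**Conclusion.** The concern holds in a bounded form. As listed, the data cannot fill the two splits as SAP 7.4 labels them. For surgery, the gap affects patients whose biologic started before enrolment, and no others. For steroids, it affects anyone treated with steroids before the recorded window, including some who start the biologic after enrolment. If absent records count as none, which is the likely result without an 'unknown' level, the error goes only towards '<3 courses' and 'non-surgical'.

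The mismatch of dates and the direction follow from the text and that one counting assumption. The size does not. The surgery illustration roughly halves the frequency under one start pattern and cuts it by about a third under another; the steroid losses range widely with the assumed rates and disease durations. None of these is an estimate for this study. The point merits a correction to the SAP, in proportion to exploratory, descriptive tables.

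**What to change.** In SAP 7.4:

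1. Assign '<3 courses' or 'non-surgical' only to patients whose recorded window covers the whole stated look-back.
2. Define the steroid split on courses recorded within a stated, observed window before the biologic start, and remove the reference to medical history from the label. The window length and the course cut-points are for the sponsor to choose.
3. Keep the 2-year surgical look-back where it is fully observed, and count any recorded operation within 2 years before the start as surgical.
4. Place all remaining patients in an explicit 'look-back incomplete' row and report its count for each split.

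This needs SAP wording and programming from recorded dates, with no new data. The cost is fewer classified patients. With a 2-year look-back, the 'non-surgical' row would hold only starts at or after Visit 1, and the documents do not show how many there are. Because step 3 lets patients with a partial look-back enter the surgical row but not the non-surgical one, the frequency of surgery should be taken only from patients with a complete look-back.

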## 2. Ustekinumab

a. By the period of time from diagnosis to biological therapy prescription:

- up to 2 years inclusive
- from 2 to 5 years inclusive
- more than 5 years

b. By the number of courses of systemic corticosteroids in medical history before biological therapy prescription:

- < 3 courses
- ≥ 3 courses

c. Depending on disease activity at the moment of biological therapy prescription:

- Crohn's disease, the Harvey-Bradshaw index:

- < 5 points
- 5-16 points
- >16 points

- Ulcerative colitis, the Partial Mayo Score:

- 0 scores
- 1-2 scores
- 3-5 scores
- ≥ 6 scores

Protocol ID	MACS-2017-102279	STATISTICAL ANALYSIS PLAN	Page 19 of 41	
IP	N/A		Date	30.12.2021
ID	MACS-2017-102279_SAP		Version	v1.2 final

### 3. Anti-TNF- $\alpha$

- a. By the period of time from diagnosis to biological therapy prescription:
  - up to 2 years inclusive
  - from 2 to 5 years inclusive
  - more than 5 years
- b. By the number of courses of systemic corticosteroids in medical history before biological therapy prescription:
  - < 3 courses
  - $\geq$  3 courses
- c. Depending on disease activity at the moment of biological therapy prescription:
  - Crohn's disease, the Harvey-Bradshaw index:
    - < 5 points
    - 5-16 points
    - >16 points
  - Ulcerative colitis, the Partial Mayo Score:
    - 0 scores
    - 1-2 scores
    - 3-5 scores
    - $\geq$  6 scores

### 4. Tofacitinib

- a. By the period of time from diagnosis to biological therapy prescription:
  - up to 2 years inclusive
  - from 2 to 5 years inclusive
  - more than 5 years
- b. By the number of courses of systemic corticosteroids in medical history before biological therapy prescription:
  - < 3 courses
  - $\geq$  3 courses
- c. Depending on disease activity at the moment of biological therapy prescription:
  - Crohn's disease, the Harvey-Bradshaw index:

Protocol ID	MACS-2017-102279	STATISTICAL ANALYSIS PLAN	Page 20 of 41	
IP	N/A		Date	30.12.2021
ID	MACS-2017-102279_SAP		Version	v1.2 final

➤ < 5 points

➤ 5-16 points

➤ >16 points

• Ulcerative colitis, the Partial Mayo Score:

➤ 0 scores

➤ 1-2 scores

➤ 3-5 scores

➤ ≥ 6 scores

**Subgroups depending on the use of drugs in the first- and second-line therapy**

- a. Ustekinumab in the first line, vedolizumab in the second line
- b. Ustekinumab in the first line, anti-TNF- $\alpha$  in the second line
- c. Ustekinumab in the first line, tofacitinib in the second line
- d. Vedolizumab in the first line, tofacitinib in the second line
- e. Vedolizumab in the first line, ustekinumab in the second line
- f. Vedolizumab in the first line, anti-TNF- $\alpha$  in the second line
- g. Anti-TNF- $\alpha$  in the first line, ustekinumab in the second line
- h. Anti-TNF- $\alpha$  in the first line, vedolizumab in the second line
- i. Anti-TNF- $\alpha$  in the first line, tofacitinib in the second line
- j. Tofacitinib in the first line, ustekinumab in the second line
- k. Tofacitinib in the first line, anti-TNF- $\alpha$  in the second line
- l. Tofacitinib in the first line, vedolizumab in the second line

**By the route of anti-TNF- $\alpha$  administration**

- a. Subcutaneous administration
- b. Intravenous administration

**Depending on surgical treatment within ≤ 2 years before biological therapy prescription:**

- a. Surgical patients
  - With post-operative anti-relapse biological therapy (CD)
  - Without post-operative anti-relapse biological therapy (CD)
- b. Non-surgical patients

Protocol ID	MACS-2017-102279	STATISTICAL ANALYSIS PLAN	Page 21 of 41	
IP	N/A		Date	30.12.2021
ID	MACS-2017-102279_SAP		Version	v1.2 final

**Depending on response to immunosuppressive therapy**

- a. Absence or loss of response
- b. Maintenance of response

**Depending on the age of onset:**

- a. < 18 years
- b. 18–40 years
- c. 41–60 years
- d. 60 years

**Depending on age at the time of inclusion in the study:**

- a.  $\leq$  60 years
- b. 60 years

**Depending on Body Mass Index**

- a. < 18.5 kg/m^2
- b. 18.5–24.9 kg/m^2
- c. 25–29.9 kg/m^2
- d. 30–34.9 kg/m^2
- e. 35–39.9 kg/m^2
- f.  $\geq$  40 kg/m^2

Protocol ID	MACS-2017-102279	STATISTICAL ANALYSIS PLAN	Page 22 of 41	
IP	N/A		Date	30.12.2021
ID	MACS-2017-102279_SAP		Version	v1.2 final

## 8 STATISTICAL DATA PROCESSING

### 8.1 Statistical methods

#### 8.1.1 General information

Statistical analysis will be conducted using the software package Microsoft R Open version 4.0.2 from Microsoft R Application Network (MRAN) (<https://mran.microsoft.com>). Exact version of the software will be determined at the time of first interim analysis and will remain unchanged throughout the study. Version control for the software and related R packages used for statistical data processing will be performed using the CRAN Time Machine from Microsoft (or the purpose of reproducibility, MRAN hosts daily snapshots of the CRAN R packages and R releases as far back as Sept. 17, 2014). Statistical analysis will take data type and scale for each parameter when describing and analyzing the data.

Quantitative data (both continuous and discrete, if applicable) will be presented using the following parameters:

- Number of non-missing observations (n);
- Arithmetic mean (M);
- Standard deviation (SD);
- 95% confidence interval for the mean (95% CI);
- Median (Me);
- 25th percentile;
- 75th percentile;
- Minimal value (min);
- Maximal value (max);

Qualitative data including binary and categorical variables will be presented as number of cases per category, frequency for the category (relative to the non-missing number of observations), as well as 95% exact binary confidence interval calculated using Clopper-Pearson method (binary data) or Goodman method (categorical data).

Time-to-event data will be presented as median, 25th and 75th percentiles as well as graphically as Kaplan-Meyer survival curves with log-log 95% confidence intervals.

No statistical tests are planned for the primary endpoint of this study as all outputs will be purely descriptive. However, 95% significance level will be applied for all confidence intervals calculated, and exploratory statistical analysis will be conducted to identify statistically significant associations between treatment patterns and outcomes.

Medical history, concomitant conditions and adverse events will be coded using the MedDRA dictionary. As version of MedDRA is updated every six months, the first interim analysis will be conducted using the most current MedDRA version, and all subsequent analyses, including the

Protocol ID	MACS-2017-102279	STATISTICAL ANALYSIS PLAN	Page 23 of 41	
IP	N/A		Date	30.12.2021
ID	MACS-2017-102279_SAP		Version	v1.2 final

final analysis, will be performed using the updated MedDRA versions and all previously analyzed data will be checked using MedDRA version comparison tool for the presence of changes from version to version and re-coded if applicable. The updated version of MedDRA used in the final analysis will be specified in the SAR. Both original and updated coding will be kept for tracking purposes.

Concomitant and prior medications will be coded with Anatomical Therapeutic Chemical Dictionary (ATC) current version.

Due to the descriptive nature of the study, all available data will be analyzed.

